## Research Design and Methods

**Participants:** The participants will be Veterans with history of TBI:  $n = 20$  will undergo the training intervention, and  $n = 20$  will participate in repeated testing without intervention. Inclusion criteria: Veterans, ages 21 to 55, with a history of TBI (as defined by the American Congress of Rehabilitation Medicine and VA, with reported plausible mechanism of head injury, loss of consciousness with some period of post-traumatic alteration in cognition), in the chronic, stable phase of recovery ( $>6$  months from injury), with residual cognitive complaints (Neurobehavioral Symptom Inventory, cognitive subscale  $>9$ ). Participants will be on stable psychoactive medications ( $> 30$  days); able and willing to participate in EEG, training and, assessments. *Common mental health comorbidities present amongst OEF/OIF/OND Veterans, such as depression and PTS (Carlson et al., 2011; Carter, 2014), will be permitted in order to address realistic aspects of recruitment (i.e. it would be unrealistic to expect a sample of 'pure TBI' amongst current generation combat Veterans) as well as a practical goal of intervention work in addressing needs of Veterans. However, participation will be limited to Veterans reporting PTS and depression symptoms below clinical thresholds (see self-report questionnaires section for more details: PCL-5 scores  $< 38$ , Weathers et al., 2013; BDI-II scores  $< 19$ ; Homaifar et al., 2009).* Exclusion criteria: Severely apathetic/abulic, aphasic, or other reasons for being unable or unwilling to participate with the training tasks; severe cognitive dysfunction; history of neurodevelopmental abnormalities; ongoing illicit drug or alcohol abuse (AUDIT $>8$ ); schizophrenia; bipolar disorder; history of other neurological disorders; current medical illnesses that may alter mental status or disrupt participation in the study; active psychotropic medication changes. There will be no restriction in regard to gender, race and socioeconomic status.

**Study design and participant flow.** Participation in the proposed study will span approximately 10-12 weeks. Participants will be recruited via IRB-approved methods, and interested candidates will undergo preliminary screening ( $\sim 1$  hr phone interview + VA records review). Eligible participants will be invited to enroll and provide informed consent approved by the IRB of VA Northern California.

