Baseline assessments of cognitive status and functioning, as well as EEG, will be conducted in weeks 1-2. Time commitment for baseline assessments is approximately 4-5 hours. Participants will then be assigned to (a) active training or (b) no training conditions in a pseudo-random order, matched across key demographic variables. The no training condition will serve to assess changes to EEG and other measurements with repeated testing in the absence of active training. This will lay a foundation for future studies that will incorporate an active comparison intervention.

Participants in active training will complete seven training sessions in weeks 3-10. Training sessions last 2 hours, and participants are requested to complete approximately 2.5 hours of additional skill practice over the course of each week outside of session (total  $\sim 4.5$  hours per week). The same overall training time will be targeted ( $\sim 32$  hours) for all individuals, although the training schedule will accommodate variations in individuals' schedules and availability over the course of  $\sim 8$ -10 weeks to maximize engagement. In the 2 weeks after training concludes, participants will complete a second round of assessments ( $\sim 3$ -4 hrs). Participants will be compensated \$20/hr for their time during the assessment portions of the study as well as for their travel expenses at \$0.55/mile for travel greater than 20 miles to and from the study site.

Enrollment will begin within 3 months of the initiation of the grant period, and continue through month 21. Data will be checked and pre-processed on a rolling basis and final analyses and reports will be completed in months 22-24.

**Training Intervention:** Training follows a manualized protocol, with seven in-person two-hour sessions (Loya et al., 2014; Rodriguez et al., 2014) and instructions to practice skill use while playing the Startup-to-CEO game for 30 minutes/day, five times per week, and to practice skill use within the context of their daily life. Game scenarios are utilized to highlight contexts where goal-directed functioning is susceptible to disruption and where skill use might be helpful. They further help facilitate discussions about skill application in personal life. In addition, twice weekly semi-structured phone check-ins are conducted to provide motivational support and reinforce skill use.

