**Pre- and Post-Training EEG:** Participants will attend testing sessions pre- and post-training. The first phase of each session measures several minutes of resting state brainwaves for use in connectivity modeling (Langer et al., 2013). Participants will complete a brief assay of self-regulation, with instructions to relax and focus on the cycle of breathing, re-directing attention if the mind wanders, as in our prior fMRI study (Arnemann et al., 2015). In the second phase, participants will perform our well-validated working memory dual task while EEG is recorded and averaged using standard methods. EEG time-frequency analyses will target the theta and alpha bands based on prior studies (Thornton & Carmody, 2009). This experiment is ideal for use in evaluating potential neural mechanisms of our targeted training, because of its sensitivity to working memory load and distractions. Data will be collected by staff in [name] lab, and EEG analysis carried out by [name], who has experience describing EEG markers and evaluating novel training approaches in clinical populations (Pineda et al., 2014).

**ERP Recording:** Continuous EEG will be recorded from 64 scalp electrodes and two electrodes placed on the left and right mastoids using the ActiveTwo Biosemi electrode system. Four electrodes placed laterally and below both eyes will record blinks and eye movements. The EEG will be sampled at 512 Hz. Biosemi uses a “common mode sense” active electrode and “driven right leg” passive electrode to form a feedback loop that serves as the “ground” electrode. All signals will be recorded using ActiView software.

**ERP Data Analysis:** Off-line analysis will be completed using Brain Vision Analyzer software. Data will be re-referenced to the average of the mastoid electrodes and bandpass filtered from 0.1 to 30 Hz (48 dB/octave). The EEG will be segmented for each trial beginning 100 ms pre-stimulus and extending to 900 ms post-stimulus onset. EEG will be corrected for blinks using the Gratton procedure; artifacts exceeding 150  $\mu$ V will be rejected. Segments will be baseline corrected and averaged with similar trials. ERPs will be

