**Sample Size Calculation:** We powered the study based on prior group differences (mtBI/PTS vs. Controls). We used data from the Sternberg task (Honzel et al., 2014) to obtain an estimate of the standard deviation of the ERP old/new effect, and expected effect size based on a mixed effects ANOVA (subject as random effect) with group as the sole explanatory variable. To estimate sample size, we used the two sample *t* test as an approximation to the mixed effects ANOVA and used the method of variance inflation to account for the additional subject factors (Hsieh et al., 2003). We powered based on the primary experimental question at 80% and will control false discovery rate at 5% (Benjamini & Hochberg 1995) at the time of analysis for tests of other design and subject factors. The Sternberg data showed a mean difference between the patient and control groups of -1.097 with residual error of 0.956 from the mixed effects ANOVA. Using these values in a two-sample *t* test for mean difference, to obtain 80% power we need a sample size of 13 per group. *This pilot study will allow us to collect data to inform power calculations for future studies.*’

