**Dual-Task Condition (Sternberg Memory Task + Arrow Flanker):** Participants will be required to perform the arrow flanker task during the delay interval of the Sternberg memory task. Nine flanker trials begin 300 to 500 ms following the presentation of each memory set. The stimulus parameters are the same as for the single-task flanker. The Sternberg probe is then presented 500 ms following the final flanker trial, and participants respond to indicate whether this item was in the previous memory set.

**Statistical Analysis:** The ERP old/new effect will be analyzed using a mixed effects ANOVA controlling for task (single, dual), set size (one, four), and time point (pre, post). The primary neuropsychological outcome measures will be included in the models as appropriate to assess changes from pre- to post-training. To examine the effects of repeated testing, differences in ERP mean amplitudes between patient groups (trained, untrained), task, and set size will be also be tested using a separate mixed effects ANOVA to control for random effects due to subject. Pre/post differences in Sternberg WM accuracy will be tested using a hierarchical generalized linear model. Time-frequency responses will be analyzed with the same mixed and linear models, with separate calculations for each frequency band, and a repeated measures model including all frequency bands.

**Predicted Results:** We predict that Veterans who show cognitive gains with training (based on neuropsychological measures) will show an increase in the ERP old/new effect in the dual task condition. Additionally, as prior work has shown that WM impairment in ADHD is characterized by decreased levels of alpha power during encoding, and compensatory increases in theta during maintenance (Lenartowicz, et al. 2014), we predict that cognitive gains will be reflected by changes in theta and alpha power over frontal scalp. Importantly, we can determine with precise temporal resolution whether the neural manifestations of training improvements occur during WM encoding, maintenance, and/or retrieval. Additional analyses will determine whether these EEG markers can predict which patients will improve with training.

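### The repeated-testing analysis compares trained with untrained participants, so a practice effect common to both arms cancels, and no pre-to-post estimate in the untrained arm is specified

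*Combined protocol and SAP*

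**What the plan says.** All references are to the combined protocol and SAP.

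- **Purpose of the untrained arm** (Research Design and Methods, study design and participant flow): "The no training condition will serve to assess changes to EEG and other measurements with repeated testing in the absence of active training". The text adds that this is groundwork for later trials with an active comparator.
- **Who is tested twice.** The 20 untrained Veterans "will participate in repeated testing without intervention" (Participants). For EEG, "Participants will attend testing sessions pre- and post-training" (Pre- and Post-Training EEG). Participants are "assigned to (a) active training or (b) no training conditions in a pseudo-random order", matched on demographic variables.
- **Analysis named for repeated testing** (EEG of Working Memory with and without a secondary attention task, Statistical Analysis): "To examine the effects of repeated testing, differences in ERP mean amplitudes between patient groups (trained, untrained), task, and set size will be also be" analysed in a mixed ANOVA of their own, with subject as a random effect. The factors listed are group, task and set size.
- **The other ERP model** (same paragraph) is a mixed ANOVA of the old/new effect "controlling for task (single, dual), set size (one, four), and time point (pre, post"). It lists no group factor and does not say whether it covers both arms or only the trained one.
- **Time-frequency responses** are to be analysed with the same models, so whatever is true of the ERP analysis carries over to theta and alpha power.

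**The concern.** The question is how much the EEG changes when people are simply tested again. The natural estimate is the pre-to-post change among those who were not trained. The analysis named for that question is instead a difference between arms. Since both arms sit the test twice, a practice effect of the same average size adds equally to each and vanishes from the difference.

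Two things are at stake. A null group difference carries no information about the size of the practice effect, yet the label invites reading it as evidence that there is none. A group difference produced by training, or by baseline imbalance, could be reported under the heading of repeated testing. Either way, the retest estimate that is meant to inform later trials is not among the analyses specified.

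**Working it through.** **Inputs from the plan.** There are 20 trained and 20 untrained participants. Sample Size Calculation gives a "mean difference between the patient and control groups of -1.097 with residual error of 0.956 from the mixed effects ANOVA". I take 0.956 as the SD of one person's score at one visit, which is how that paragraph uses it. (The same number appears in Preliminary Studies as a Cohen's d; the algebra below does not depend on it.)

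**Assumptions.** The pre-post correlation ρ is not given, so I use 0.3, 0.5 and 0.7. I use a nominal two-sided 5% level per test, because the plan states only a 5% false discovery rate for tests of other factors. The average practice effect is the same in both arms. Effect sizes are illustrative: 1.097 is borrowed from the plan's patient-control difference, 0.55 is half of it (0.5485), and 2.194 is twice it.

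**The plan's own figure.** For a two-sample t test the noncentrality is 1.097 / (0.956 × √(2/n)). At n = 12 it is 2.81 (power 76.6%) and at n = 13 it is 2.93 (power 80.1%). The stated 13 per group reproduces and is not in dispute.

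**What each contrast estimates.** Let π be the practice effect, τ the training effect, and b the baseline difference (trained minus untrained).

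- Group difference, post visit: b + (π + τ) − π = b + τ
- Group difference, visits pooled (time omitted): b + (π + τ)/2 − π/2 = b + τ/2
- Group difference in change: (π + τ) − π = τ
- Time term of the other ANOVA, both equal-sized arms: [(π + τ) + π]/2 = π + τ/2
- Time term of the other ANOVA, trained arm only: π + τ
- Pre-to-post change, untrained arm: π

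Only the last line isolates π.

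**Rejection rates.** These come from 40,000 simulated trials per setting with b = 0. Where three figures are shown, they are for ρ = 0.3 / 0.5 / 0.7.

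| Practice, training | Group, post | Group, visits pooled | Group, change | Untrained pre-post |
|---|---|---|---|---|
| 0.55, 0 | about 5% | about 5% | about 5% | 54 / 68 / 88% |
| 1.097, 0 | about 5% | about 5% | about 5% | 98.5 / 99.8 / about 100% |
| 2.194, 0 | about 5% | about 5% | about 5% | about 100% |
| 0, 1.097 | 94% | 59 / 53 / 48% | 85 / 94 / 99.5% | about 5% |

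With no training effect, every group-test rate lay between 4.8% and 5.4%. Adding a practice effect of 1.097 to the last row left its group-test rates essentially unchanged.

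**Closed-form check.** For the untrained arm with practice 0.5485, the noncentrality is 0.5485 / (0.956 × √(2(1 − ρ)) / √20) = 2.17 / 2.57 / 3.31, giving power of 54 / 68 / 88%. For the pooled group test with training 1.097, it is 0.5485 / (0.956 × √((1 + ρ)/2) × √(2/20)) = 2.25 / 2.10 / 1.97, giving 59 / 53 / 48%. Both agree with the simulation.

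**Task and set size do not recover it.** A mixed model with group, task, set size and their interactions and a random subject effect was fitted to 150 simulated trials per setting, so these rates are rough. A practice effect of 1.097 gave 4% rejection for group. A practice effect larger in the dual task gave 6% for group and 0% for group-by-task. A training effect of 1.097 gave 66% for group.

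**The case against.** The fairest defence is that this is one loosely worded sentence. The description of the untrained arm shows that its purpose is understood, and the sentence may mean that the arms are compared so that change from training can be told apart from change on retest. On that reading a between-arm comparison is a normal choice and the fault is the label. That much is fair. Even so, time point is missing from the listed factors, and the retest change itself is still not among the specified analyses.

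It can also be said that the other ANOVA has a time term and that the listed factors need not be the full model. This limits the claim to what is specified. It does not fill the gap, because that time term contains some or all of the training effect.

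Practice might differ between arms. If it does, the excess in the trained arm cannot be separated from training, so the group contrast still does not measure retest.

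Finally, this is a secondary analysis in a self-described pilot, with no bearing on visits, allocation or sample size. That is true, and it bears on priority. The retest estimate is nevertheless a stated product of the pilot.

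Three stronger readings are tempting, and the documents do not support them:

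- **A reader might infer that the sponsor will declare no retest effect after a null result.** The plan states no such rule. The misreading is possible, not planned.
- **A reader might infer that the retest estimate is lost, or that adding time to the group model would not help.** Both visits are collected in the untrained arm, and a model with group and time yields that arm's change directly. Only the between-group terms remain uninformative about retest.
- **A reader might infer that the group test dependably rejects when training works.** That depends on the effect size and on whether visits are pooled: about 94% on post values but only 48% to 59% pooled, for the same effect of 1.097.

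**Conclusion.** Wrong as written. The analysis labelled as examining repeated testing is a between-group contrast from which a common practice effect cancels. The only ERP model that lists time point does not list group. The untrained arm's pre-to-post change, which is that arm's stated purpose, is not specified.

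The cancellation is algebraic and needs only an equal average practice effect in the two arms. The rejection rates are illustrative: they rest on an SD of 0.956, assumed correlations of 0.3 to 0.7, borrowed effect sizes and a nominal 5% level, and false-discovery-rate control could only lower them. On those terms the named test has no power beyond its error rate against any shared practice effect, and it responds to training (or, with time omitted, to half of the training effect plus any baseline imbalance), which could then be mislabelled.

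**What to change.** In the Statistical Analysis paragraph of the working-memory EEG section, replace the repeated-testing sentence with a single mixed model containing group, time point, task, set size and their interactions, with subject as a random effect. From that model:

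- report the pre-to-post contrast within the untrained arm, with a 95% confidence interval, as the effect of repeated testing;
- report group-by-time as the effect of training;
- do this for the ERP old/new effect and for theta and alpha power;
- do not describe any trained-versus-untrained difference as an effect of repeated testing.

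The interval matters more than the p-value. With 20 untrained participants and the SD above, its expected half-width is 2.093 × 0.956 × √(2(1 − ρ)) / √20, which is about 0.53, 0.45 and 0.35 for ρ = 0.3, 0.5 and 0.7. A non-significant change would therefore not show that practice is absent.

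The cost is a change of wording and one contrast on data already planned. No visits or participants are added.

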quantified by computing mean amplitudes in defined latency windows relative to a 100 ms pre-stimulus baseline. The primary measure will be the ERP “old/new effect” elicited during memory retrieval, time-locked to probe onset. This will be quantified by subtracting mean amplitude for Old – New probes (300-500 ms post-stimulus) at midline electrodes (Honzel et al., 2014).

**EEG Time-Frequency and Network Analysis:** Off-line analysis for resting state and dual task data will be performed in the EEGLAB Matlab toolbox (Delorme & Makeig, 2004). Data will be filtered with bandpass limits of 0.1 to 55 Hz using a standard FIR filter and re-referenced to the average of mastoid electrodes. Periodic artifacts, such as eyeblinks, will be removed using the Infomax Independent Component Analysis (ICA) algorithm. Remaining data will be further band filtered into four frequency bands (theta: 4-8 Hz, alpha: 8-13 Hz, beta: 15-30 Hz, & gamma: 30-55 Hz), and power envelope and phase angle will be extracted with a Hilbert transform.

Resting state connectivity will be calculated over two second epochs using a graph theoretical approach comparing each pair of electrodes in each frequency band, based on correlation of band power changes, and degree of phase coherence. *As we are working with resting state data, we have no a priori hypothesis about directionality of information flow. Therefore, correlations of these measures will suffice (Bastos & Schoffelen, 2016), thereby decreasing computation demands.* Spurious connectivity will be corrected by eliminating neighboring electrode connections and ignoring electrode pairs with 0 degrees of phase lag. Remaining electrode pairs will be adjusted to a common threshold to control number of network connections across patients. From these binarized connectivity matrices, modularity and characteristic path length (CPL) will be calculated using the Matlab toolbox, EEGNET (Hassan, et al. 2015). Time-frequency responses to dual task conditions will be calculated using Hilbert transformed data, epoched and averaged over the same time window and baseline as ERP analysis.

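### The only ERP model that names group is written on mean amplitudes with no old/new and no time-point term, so no planned ERP model clearly tests whether change in the primary ERP measure differs between trained and untrained participants

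*Combined protocol and SAP*

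**What the plan says.** All references are to the combined protocol and SAP.

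- **ERP Data Analysis (Research Design and Methods).** ERPs in general are "quantified by computing mean amplitudes in defined latency windows relative to a 100 ms pre-stimulus baseline". One derived quantity is then singled out: "The primary measure will be the ERP “old/new effect” elicited during memory retrieval, time-locked to probe onset". Its definition follows: "This will be quantified by subtracting mean amplitude for Old – New probes (300-500 ms post-stimulus) at midline electrodes".
- **Statistical Analysis (EEG of Working Memory with and without a secondary attention task), first model.** "The ERP old/new effect will be analyzed using a mixed effects ANOVA controlling for task", set size and time point. No group term is listed, and the paragraph does not say which participants enter.
- **Same paragraph, second model.** To look at repeated testing, "differences in ERP mean amplitudes between patient groups (trained, untrained), task, and set size will be also be tested" in a separate mixed effects ANOVA with subject as a random effect. The outcome is mean amplitude. Group, task and set size are listed; probe type and time point are not.
- **Study design and participant flow.** "The no training condition will serve to assess changes to EEG and other measurements with repeated testing in the absence of active training".
- **Predicted Results.** Veterans who gain cognitively from training "will show an increase in the ERP old/new effect in the dual task condition".
- **Sample Size Calculation.** The study is sized on a two-group difference in the old/new effect: 1.097 in absolute value, residual error 0.956, 80% power, 13 per group. The Participants paragraph plans 20 per group.

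**The concern.** The untrained arm is there to separate training from retesting. For the primary ERP measure, that requires comparing the pre-post change in the old/new effect between the arms. The first model has the right outcome and a time point but no group term. The second has group, but its stated outcome is a different quantity and it has no time point. Neither model, as listed, contains the comparison.

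Two gaps sit in the same sentence:

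- **Outcome.** Without a probe-type factor, a model on mean amplitude estimates group differences in overall amplitude, not in the Old-New contrast.
- **Time.** Without a time point there is no group-by-time term, whichever outcome is meant.

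At stake is whether an increase in the old/new effect among trained Veterans can be attributed to more than repeated testing. If the sentence stays open to two readings, the choice between them could be made after the data are seen.

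**Working it through.** **Step 1. The two ERP models side by side**

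| | First model | Second model |
|---|---|---|
| Outcome | old/new effect | ERP mean amplitudes |
| Group | not listed | listed |
| Time point | listed | not listed |
| Probe type | built into the outcome | not listed |
| Task, set size | listed | listed |

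The term needed is group-by-time on the old/new effect or, equivalently, group-by-time-by-probe type on mean amplitude. Neither column supplies it.

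**Step 2. Reproduce the plan's figure**

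Inputs from Sample Size Calculation: difference 1.097, SD 0.956. No alpha is stated for this calculation, so 0.05 two-sided is assumed. Standardised difference = 1.097 / 0.956 = 1.147. The two-sample t test (noncentral t) needs n = 12.96, so 13 per group, with power 80.1% at 13. The stated 13 reproduces. At the planned 20 per group, power is 94.2%.

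**Step 3. What mean amplitude sees of a shift in the old/new effect**

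Let the Old and New responses shift by dOld and dNew.

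- Shift in the old/new effect = dOld − dNew.
- Shift in amplitude averaged over probe type = (dOld + dNew) / 2.

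If only Old rises by 1.097, the averaged amplitude moves 1.097 / 2 = 0.5485. If Old rises and New falls equally, it moves 0 and power equals alpha (5%).

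The SD changes too. Let each probe type have SD a and let their within-person correlation be r (not given in the plan; assumed). Then:

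- SD of the old/new effect: 0.956 = a√(2(1 − r)), so a = 0.956 / √(2(1 − r)).
- SD of the averaged amplitude = a√((1 + r)/2).

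Only Old rises, 20 per group:

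| Assumed r | SD of averaged amplitude | 0.5485 / SD | Power |
|---|---|---|---|
| 0 | 0.478 | 1.147 | 94% |
| 0.5 | 0.828 | 0.663 | 53% |
| 0.8 | 1.434 | 0.382 | 22% |
| 0.9 | 2.084 | 0.263 | 13% |

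The comparator, with the old/new effect as outcome, is 94%.

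**Step 4. Changing the outcome alone is not enough**

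Take the old/new effect as outcome but keep no time point, so that the group effect pools pre and post. With no group difference at baseline, the shift is again 1.097 / 2 = 0.5485. With an assumed pre-post correlation ρ, the SD of the pooled value is 0.956√((1 + ρ)/2), and the SD of the change is 0.956√(2(1 − ρ)).

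| Assumed ρ | Power, pooled group effect | Power, group-by-time |
|---|---|---|
| 0.3 | 59% | 85% |
| 0.5 | 53% | 94% |
| 0.7 | 48% | 99.5% |

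**The case against.** The strongest reply is that the sentence is shorthand. The old/new effect is itself a difference of mean amplitudes, so an author could refer to it in those words. The sample size section, which sizes a two-group comparison of the old/new effect, suggests that this was the intended outcome. Nothing in the plan says Old and New trials will be pooled; segments are to be averaged with similar trials, which suggests averages kept by condition.

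This reading is possible, and it rules out calling the sentence a proven change of outcome. It does not clear the sentence. The differences it names are between groups, task and set size, not between probes; the sentence opening the same paragraph names the old/new effect outright; and the shorthand reading leaves the time point missing.

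Three stronger readings are tempting and are not supported:

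- **That untrained participants appear only in the second model.** The plan does not exclude them from the first. It lists no group term and states no analysis population, although its reference to change across training hints at trained participants. What can be said is that the second is the only ERP model that names group.
- **That the group test is bound to lose power.** In the Old-only case the loss depends on an Old-New correlation that the plan does not give, and there is none at a correlation of 0. The zero-shift case needs exactly opposite movements, which the plan does not predict.
- **That arousal or electrode contact could be mistaken for a training effect.** Nothing in the plan suggests the arms would differ on these, and segments are baseline corrected.

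It is also fair to say that this is a self-described pilot. That limits the consequences, but the correction is small enough to make anyway.

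**Conclusion.** The concern holds in this form: as written, no planned ERP model compares trained and untrained participants on the pre-post change in the old/new effect. If the outcome wording is shorthand, half the problem goes away and the missing group-by-time term remains. The change should be made before analysis.

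The missing terms follow from the text and rest on no assumption. The size is illustrative only. It uses a patient-control difference as a scale rather than a training effect, takes 0.956 as the SD because the plan labels it residual error (Preliminary Studies reports the same number as a Cohen's d for the dual-task contrast), and assumes a two-sided alpha of 0.05 and the correlations shown. On those terms, the literal reading gives anything from no loss (94%) to severe loss (13%) when only Old rises. Correcting the outcome without adding time point leaves about 48% to 59%, against 85% to 99.5% for group-by-time.

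**What to change.** Replace the two ERP models with one mixed model:

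- **Outcome:** the old/new effect (Old minus New mean amplitude, 300-500 ms, midline electrodes).
- **Terms:** group, time point, task, set size and group-by-time, with a random subject effect.
- **Key test:** the group-by-time contrast in the dual-task condition, matching the predicted result.
- **Participants:** state that both arms enter.

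An equivalent alternative keeps mean amplitude as the outcome, adds probe type as a within-subject factor, and tests group-by-time-by-probe type.

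The cost is a sentence or two in the plan. No new data, participants or change to the planned 20 per group are needed, and there is no material downside.
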